We have designed an approach that allows us not only to collect essential information about community, provider, and patient-relevant impediments to viral testing but also to meet the critical need to increase testing in testing deserts in Oklahoma as rapidly as possible. We believe that a singular focus on one testing strategy will be ineffective in truly understanding the barriers to testing. No one strategy would be effective in reaching all of the population, due to issues such as lack of access to a primary care provider, lack of insurance, transportation, available time, or individual/community perceptions on testing itself (e.g., safety, necessity, availability, trust). Thus, we have chosen to develop the Community- engaged Approaches to Testing in Community and Healthcare settings for Underserved Populations (CATCH-UP) program with practice-based and community-based approaches to maximize the reach of the RADx-UP consortium, broaden the potential perspectives that could be captured, and compare the effectiveness of strategies. Rather than developing an inflexible practice-based intervention *a priori*, we believe that the ever-changing barriers, attitudes and conditions in the pandemic, as well as the development and deployment of more effective diagnostic technologies over the next few months, necessitate a pragmatic approach in which we initiate increased testing quickly while simultaneously collaborating with stakeholders and collecting participant survey data in real-time, which we believe will allow the intervention to evolve to changing needs, and provide rapid-cycle evaluation of effectiveness of these activities to provide timely feedback to our partners and other RADx-UP initiatives.

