the beginning of the project. Subjects for this research project will include primary care clinicians and their office staff. They will be interviewed and observed, and their performance will be evaluated. Each practice will be asked to complete one approximately 15-minute Practice Characteristics Assessment twice (at enrollment and at the end of the study).

Each clinician and office staff member will be asked to complete a 10-minute Provider Survey at baseline and quarterly thereafter. The Practice Characteristics Assessment and Provider Surveys will be delivered to practice staff via an email that includes a web-based REDCap survey link. Medical record data will be abstracted from each practice for performance feedback and outcome measure assessment using EHR registry reports. Each practice will receive support from academic detailers and practice facilitators and performance reports to improve their processes of care.

Patients will be involved in two ways, through completion of patient surveys and through retrospective abstraction of their medical record data for performance tracking and reporting. Patients offered SARS-CoV-2 testing (at either a participating primary practice or mobile testing unit) will be provided a flyer that includes both a QR code and URL to the Patient Survey in REDCap. This survey will be completed anonymously and set up to ensure that patients can only complete the survey one time.

Key Informant Interviews (KII) and Patient/Provider Surveys

KII will be conducted over Zoom at the beginning and end of the project, with community stakeholder, provider, and patient representatives to help inform the facilitators and barriers to be included in the Practice/Provider and Patient Surveys with a focus on identifying and capturing those encountered by underserved, vulnerable populations. Participants will be consented electronically via REDCap prior to conducting the interviews. Provider and Patient Surveys responses will also be monitored on a monthly basis and shared with the SAB and CAB to identify whether adaptations to our program are needed.

Practice/Provider Surveys will be delivered to practice staff via an email that includes a web-based REDCap survey link. When offered testing, patients will be given a flyer with a QR code and web-based link to complete the Patient Survey via REDCap. The survey link will be unique for each flyer to ensure that an individual can only complete the survey once.

Testing Capacity

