We anticipate that approximately 5,000 individuals will participate in the limited serology study through the community-based testing sites for the CATCH- UP program. Individuals 13 years of age or older are eligible to participate.

Given the minimal risk of the study and because study participants will already be at the site to participate in community viral testing, we will not provide compensation to the individuals for participation in the study.

Consortium Data Reporting Unit

OSCTR and OPHIC have the experience and capability to collaborate with other RADx-UP grantees to share effective implementation strategies and for reporting of protocols, survey results, testing data, referral data, demographics, and other required documentation to the RADx-UP Coordinating and Data Collection Center (CDCC). As described in Aim 3, we will collaborate closely with the CDCC to share our evaluation efforts, modify data collection plans to align with the national effort, and report data at intervals set by the CDCC.

Practice-based SARS-CoV-2 Testing Strategy

The goal is to provide technical support to Oklahoma primary care practices to help them implement a culturally-responsive approach to SARS-CoV-2 testing based on best available evidence and current guidelines. The approach will include development of implementation support resources for testing and risk mitigation strategies to meet the needs of vulnerable populations. We are instituting a pragmatic approach that allows continuous adaption to changing guidelines, testing protocols and availability, and information learned from our provider network and the broader RADx-UP community. We will assist practices to integrate tailored SARS-CoV-2 testing protocols and resources into their workflows through our proven methodologies of academic detailing from peer- physician experts, practice change facilitation through QI implementation professionals, and health information technology support.

Scope of testing

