The practice-based testing strategy in CATCH-UP aims to assist practices to increase their ability to test patients, either through existing laboratory relationships, public health authority testing, or POC diagnostics implemented at the practice. Each individual offered a SARS-CoV-2 test will be provided a flyer with a description of the initiative and a unique link to the REDCap survey. We will adapt to ongoing disease outbreaks and community needs and focus heavily on rural primary care practices. Based on the average number of providers in rural practices and daily case loads, we anticipate that this aim will result in approximately 60,000 viral tests performed in the first year of implementation.

SARS-CoV-2 Testing Implementation Design

The nature of this pandemic has necessitated a rapid increase in testing to control the spread of the disease. Our goal is to develop a pragmatic approach that will focus on increasing evidence-based testing that is responsive to changing CDC guidelines, to assist practices in implementation of high-quality POC diagnostic tests emerging from commercial enterprises, the RADx- Advanced Technology Platforms, and/or the Point-of- Care Technology Research Network, and to collect essential data on attitudes, facilitators, and barriers to COVID-19 testing. This approach allows us to change the approach as necessary to adapt to findings from our own study and other RADx-UP projects and to design a more extensive implementation study for the proposed second phase of RADx-UP. The practice-based implementation in CATCH-UP will focus on reducing missed opportunities for testing. We will provide academic detailing at the beginning of our intervention using updated COVID-19 information in order to impact knowledge, attitudes, and skills with evidence-based sources, recognizing that some clinicians may still have beliefs that COVID's impact is "not concerning." While some clinicians with such a perspective may decline to participate, others may still be interested in providing increased testing services for their clients. In such a case, the practice's and their patients' perspectives may be extremely important for designing truly rigorous, adaptive approaches to testing.

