We will enroll 50 practices, which is approximately 3% of the primary care practices in Oklahoma. Practices will be defined as clinician-staff units that work together to deliver care to a population of patients. These care units may be a 'pod' or 'clinic' within a larger health system with multiple practices located at the same street address of a medical building. The practice, or microsystem, has the responsibility and capacity to implement Quality Improvement (QI) interventions with or without corporate or larger group assistance. We will prioritize small- and medium-size primary care practices (<10 clinicians) to participate in this project. A practice facilitator (PF) will contact interested practices to screen for eligibility and arrange a date for enrollment, if applicable. During in-person enrollment, participating clinicians and office staff will receive additional information and be able to ask questions and express concerns about the project. Those still interested will sign an informed consent document and a lead clinician and participating staff will complete baseline surveys.

Patients undergoing SARS-CoV-2 testing will be given a card/flyer with information about participating in surveys about attitudes towards COVID-19 and barriers and facilitators of testing. Consent for low-risk survey participation will occur through a REDCap form. We do not plan repeated survey measures and thus retention is not applicable.

K. Risks and Benefits

Our study focuses on the translation of evidence-based guidelines into practice. The major risk to the clinicians and office staff is loss of productivity and income. It will take some time to complete enrollment forms and questionnaires and help the practice facilitators and medical record abstractors access the performance data. In addition, the level of clinician and practice performance will be known to the research team, which if below average, might make practices' staff feel uncomfortable. The risks to patients are minimal. They involve risks associated with abstraction of their records (confidentiality) and temporary disruptions in services associated with efforts to improve care processes. There may also be concerns of loss of confidentiality when completing the Patient Surveys.

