Title of Project: Community-engaged Approaches to Testing in Community and Healthcare settings for Underserved Populations (CATCH-UP)

Principal

Investigator: [name], PhD, Oklahoma Clinical & Translational Science Institute

Co-Investigators: [name]; Department of Family Medicine

[name], MPH; Department of Medical Informatics

[name]; Oklahoma Clinical & Translational Science Institute

Statistical Methods:

Descriptive statistics and qualitative summaries will be reported to summarize implementation process measures (type, dose, frequency, and sequencing of provided support strategies) and the facilitators and barriers of implementation.

We will calculate descriptive statistics for all Aim 1 measures and will perform formal hypothesis testing to compare pre- versus post-implementation provider- level, care process, and patient-level outcomes at the patient and practice levels. In addition to this pre-post analysis, trends in testing rates will be explored. A mixed effects linear regression model will be fit to explore changes in testing rates over time relative to the control period (0 months on intervention), accounting for correlation among repeated measures on the same practice and among practices nested within PFs will be accounted for using random effects.³⁸

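### The trend model has no term for programme changes or point-of-care go-live, so a step gain from either can look like gradual learning

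*SAP*

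**What the plan says.** Several parts of the Protocol make the intervention adaptive. Under Practice-based SARS-CoV-2 Testing Strategy (section D): "We are instituting a pragmatic approach that allows continuous adaption to changing guidelines, testing protocols and availability". Under SARS-CoV-2 Testing Implementation Design: "This approach allows us to change the approach as necessary to adapt to findings from our own study and other RADx-UP projects". Under Key Informant Interviews and Patient/Provider Surveys, survey responses are to be "monitored on a monthly basis and shared with the SAB and CAB to identify whether adaptations to our program are needed". Testing Capacity says that practices begin with their existing laboratories and will be helped to adopt POC systems of their own choosing as these reach the market.

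Section C says the team believes this approach will "provide rapid-cycle evaluation of effectiveness of these activities". Goal 5 under Program Evaluation and Dissemination is to establish how effective the different testing modalities are.

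Protocol section M and the SAP carry the same statistical text. Pre- and post-implementation outcomes are compared by formal tests, and then: "In addition to this pre-post analysis, trends in testing rates will be explored". The trend model will "explore changes in testing rates over time relative to the control period (0 months on intervention"), with correlation among repeated measures on a practice and "among practices nested within PFs will be accounted for using random effects". The coding of months (linear or categorical) is not stated. Type, dose, frequency and sequence of support are summarised descriptively and are not linked to testing rates.

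On timing, section J has a facilitator contact each interested practice and "arrange a date for enrollment". The spread of start dates is not given.

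**The concern.** When practices start on different dates, a given month on intervention falls on different calendar dates. Month 4 may be the initial programme in an early practice and a revised one in a late practice. The share of practices on the revised programme therefore rises with months on intervention even if exposure itself does nothing. A model whose only time axis is months on intervention turns that rising share into a curve that resembles slow uptake. A POC go-live that raises testing at once in each practice, but on different dates, has the same effect.

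The pre-post comparison does not help, because it pools every version of the programme into one post period.

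At stake is the interpretation. A reader could conclude that the support needs many months to work when one change produced the whole gain, or could credit a change when the support was working from the start. The Protocol hopes to use this phase to design a larger second-phase study, where that distinction would be useful.

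**Working it through.** The documents give no effect size, variance or sample-size figure for this model, so there is no stated result to reproduce. What follows shows the mechanism under stated assumptions.

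**Inputs from the documents.** 50 practices (Protocol section J). Facilitation of 3 + 6 = 9 months (Practice Facilitation). Time term: months on intervention, with 0 as control (SAP).

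**Assumed.** Monthly data; start months spread evenly; one programme-wide change that adds 10 points to the testing rate; no effect of the initial programme; no learning; no pandemic trend unless stated.

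**1. Staggered starts, categorical months.** Take starts over months 0 to 6, 3 control months and a change at calendar month 6. Intervention month m of a practice starting in month s falls in calendar month s + m − 1, so the practice is on the changed programme when s ≥ 7 − m. The 50 practices fall into start groups of 8, 7, 7, 7, 7, 7 and 7.

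- Expected effect at month m = 10 × 7m/50 = 1.4m for m = 1 to 6, and 10 from m = 7.
- Result: 1.4, 2.8, 4.2, 5.6, 7.0, 8.4, 10, 10, 10.

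The truth is a single jump; the fitted curve is a ramp.

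**2. Varying the spread.** Here there is one control month, the change is at calendar month 5, and calendar month = s + m. Mean gain at months 0 to 9 on intervention:

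| Start spread (months) | Gain |
|---|---|
| 0 | 0, 0, 0, 0, 0, 10, 10, 10, 10, 10 |
| 3 | 0, 0, 2.4, 5.0, 7.4, 10, 10, 10, 10, 10 |
| 6 | 0, 4.2, 5.6, 7.0, 8.4, 10, 10, 10, 10, 10 |
| 9 | 0, 6, 7, 8, 9, 10, 10, 10, 10, 10 |

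With simultaneous starts and categorical months the jump stays visible, but it is fully confounded with calendar time.

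**3. Linear months.** For spreads of 0, 3, 6 and 9 months and a change at month 5 or 8, the false slope is 0.85 to 1.52 points per month. In 150 simulated datasets for each combination of spread 0, 6 or 9 with change month 5 or 8 (practice SD 8, facilitator SD 3, residual SD 6), it was significant every time. The distortion arises here even with simultaneous starts.

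**4. Does a programme-wide adaptation indicator repair it?** In those simulations, adding an indicator for being on intervention after the change brought the slope to about 0 and gave a step of 9.7 to 10.0. No pandemic trend was simulated, so this does not show that the indicator isolates an adaptation. In the design of step 1 the last practices begin intervention in month 6, so no control month remains at or after the change, and the indicator equals calendar month 6 or later in every row. Two consequences follow:

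- With a true adaptation effect of 0 and a pandemic step of 10 at month 6, the model returns an adaptation effect of 10.0 and month effects of 0.
- With calendar-month effects included, the columns are 50 practices + 9 exposure months + 17 calendar contrasts (18 calendar months) = 76. The rank is 76 with or without the indicator, so its effect cannot be estimated.

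With the same starts and a change at months 3 to 5, when some practices are still in control, the indicator is estimable alongside calendar months; at months 6 to 8 it is not.

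**5. Practice-specific POC go-live.** With go-live dates assumed to vary among practices, the POC indicator stayed estimable with full calendar-month effects for start spreads of 0, 3, 6 and 9 months, and without noise it returned the true effect.

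**The case against.** The strongest reply is that the model is labelled exploratory, sits beside the pre-post tests and carries no planned claim about which version worked. The Protocol, in its account of the OPHIC support strategy, also says it is not testing the effects of individual implementation components, because these are regarded as established. Both points stand and limit the importance of the issue. The disclaimer does not fully cover the concern, however: it is about the established support components, whereas POC adoption and mid-study protocol changes are new, and goal 5 asks about testing modalities directly.

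A second reply is that the ramp depends on facts the documents do not give. That is correct. Individual enrolment dates make some staggering likely but do not establish its extent, and the month coding is unstated. Many small adaptations, which continuous adaptation would suggest, could also produce a gain that really is gradual.

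A reader might go further and infer that the rapid-cycle evaluation cannot be delivered at all. The documents do not support that. The promise is worded as a belief and tied to real-time survey data and stakeholder collaboration, not to the mixed model. Monthly survey review, quarterly practice dashboards, the facilitators' electronic practice records and the planned analysis of their notes all provide feedback. What is missing is narrower: a quantitative method relating a dated change to testing rates.

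**Conclusion.** The point holds in a limited form. The programme changes by design, the only trend model has months on intervention as its sole time term, and no planned quantitative analysis links a programme change or a POC go-live to testing rates. If starts are staggered or months are linear, a step can appear as gradual learning. Under the assumed 10-point step, the false pattern is a climb of 1.4 points per month over six months (categorical months, starts over 0 to 6) or a slope of 0.85 to 1.52 points per month (linear months). Step size, change dates, start spread and SDs are illustrative; the mechanism does not depend on their exact values.

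A reader might also infer that adding a programme-wide adaptation indicator would recover the adaptation effect. The month-6 example must not be used as proof of that: there the indicator is indistinguishable from calendar time and would credit a pandemic surge to the programme. The part of the remedy that holds up best is the practice-specific POC indicator, provided go-live dates differ among practices. Overall this is an inexpensive improvement to an exploratory analysis. It does not invalidate the study.

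**What to change.** 1. Keep a dated log of programme-wide adaptations and of each practice's POC go-live, from the first enrolment onwards. Facilitators already document practice contacts in the electronic practice record, so this is mainly one extra dated field and one central list. Dates not logged at the time may be hard to reconstruct.
2. State in the SAP that months on intervention are categorical. Add calendar-month terms and a time-varying, practice-specific POC go-live indicator to the mixed model.
3. Report testing rates by programme version descriptively, as the quantitative part of the rapid-cycle evaluation.
4. Fit a programme-wide adaptation indicator only where some practices are still in their control period at the adaptation date. Otherwise state that the change cannot be separated from calendar time, and make no effect claim.
5. If all practices start together, say that months on intervention and calendar months cannot be separated either.

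The cost is SAP wording, the log and some extra parameters: one for POC, plus the calendar terms (17 in the 18-month illustration). Two limits remain. Practices choose when to adopt POC testing, so its estimate is observational. Programme-wide changes made after the last practice has started stay confounded with the pandemic.
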